### 9.3. Variables

Data from the registry networks will be provided for inclusion in this study, as available. Follow-up data is anticipated to be available from the registry networks as per their respective observational plans depending on local clinical practice.

#### Exposure

- Tofersen exposure (dose and duration), as reported in the registry data.

#### Primary Endpoints

- Demographic and clinical characteristics at the corresponding index date for treated and untreated participants for each objective:
  - Demographics (e.g., age, sex, race/ethnicity or grandparental origin, weight, height, BMI, family history of ALS).
  - Clinical characteristics (e.g., age at diagnosis, age at symptom onset, Revised El Escorial classification, phenotype, *SOD1* mutation type).
  - Medical history as available.
  - Concomitant medications (e.g., medication name, dose and unit, start and stop dates).
  - Disease history (e.g., ALSFRS-R scores, history of ventilation [invasive, non-invasive], tracheostomy, feeding tube).
  - Pregnancy status.
- SAEs (e.g., event name, SAE start and stop date, whether SAE required hospitalization, outcome of SAE etc.).

#### Secondary Endpoints

- Changes in medical history and new comorbid conditions, medications (new or changed medications during follow-up), vital status, pregnancy status and pregnancy outcome.
- Treatment discontinuation and reported reasons for discontinuation.

[REDACTED]

- [REDACTED]
- [REDACTED]
  - [REDACTED]

CONFIDENTIAL

The information contained herein may not be used, disclosed, or published without the written consent of Biogen MA Inc.

- [REDACTED]
- [REDACTED]
- [REDACTED]

#### 9.4. Data Sources

Disease registries have been previously used to assess the long-term safety in post marketing commitments requested by the US FDA and the EMA. This study focuses on the secondary use of data from 2 large networks of ALS disease registries, the TRICALS network's Precision-ALS programme [McFarlane 2023] and ALS/MND NHC [Berger 2023]. These data sources are networks of ongoing longitudinal ALS disease registries. Individual participant-level data will be collected at routine clinic visits by each registry network (Section 9.3). In advance of initiation of this study, both networks have been engaged to implement treatment and SAE data collection in their registries. The Precision-ALS data platform was developed by a consortium comprising international clinicians from the European ALS Research entity TRICALS working closely with computational data and scientists based in the Science Foundation Ireland-funded ADAPT research centre in Ireland [ADAPT 2024]. TRICALS is the world's largest network of specialty ALS centres, collecting and combining participant data from centres in multiple countries across Europe. The Precision-ALS programme is a research platform, consisting of a longitudinal data collection infrastructure based on electronic medical records as well as primary data collection for some variables. Precision-ALS includes ALS referral centres across multiple European countries. Precision-ALS has collated data from 21,000 people living with ALS from 9 participating sites [McFarlane 2023; Precision ALS 2024]. As the Precision-ALS platform expands, additional countries may be considered for inclusion in the platform and study. ALS/NMD NHC is an established multidisciplinary clinic-based registry network that prospectively and longitudinally captures important clinical information about the disease process from people living with ALS. The ALS/NMD NHC consists of academic medical centres in the United States and Europe. However, to avoid potential duplication of data from national registries already included in the Precision-ALS programme, only data from centres in the United States will be included. Over 2100 people living with ALS have enrolled in this natural history study. Data collection, curation, and analysis is through NeuroBANK, a flagship clinical research platform which is run by the Neurological Clinical Research Institute at Massachusetts General Hospital [Berger 2023; data4cures 2024].

#### 9.5. Study Size

Data will be extracted on all *SODI*-ALS cases enrolled or entering in the Precision-ALS platform and ALS/MND NHC registry networks at study start and data on all incident *SODI*-ALS cases enrolling in the registry during the first 5 years of the study. Thus, participants present or entering the registry networks during the first 5 years of the study may be included in the analyses. Given the difficulty in predicting enrolment of

CONFIDENTIAL

The information contained herein may not be used, disclosed, or published without the written consent of Biogen MA Inc.

*SODI*-ALS cases, the study will monitor enrolment and reassess the enrolment period duration while the study is ongoing.

For a 5-year enrolment period, assuming a total of 25 *SODI*-ALS cases per year could be enrolled, approximately 125 cases could be expected across both registry networks. Participants are expected to be followed in the registry networks as part of their respective observational plans until death or loss to follow-up, regardless of tofersen treatment status. Assuming a median follow-up time of approximately 2 years [Opie-Martin 2022], an enrolment of 25 cases per year, and an estimate of 40% tofersen treatment proportion, 100 person-years of follow-up data could be expected among tofersen-treated participants which will allow evaluation of the incidence of serious neurological events. Therefore, the target study size is at least 100 person-years of follow-up from tofersen-treated participants or at least 125 total *SODI*-ALS cases (tofersen-treated or untreated) during the first 5 years of the study. The enrolment period is currently planned for a minimum of 5 years, and the suitability of that time frame will be reassessed during the study.

Limited data are available on the expected incidence of serious neurologic events. Using findings from the 147 tofersen treated (100 mg) participants in the Study 233AS101 (EudraCT number: 2015-004098-33) and Study 233AS102 (EudraCT Number: 2016.003225-41) integrated population over approximately 2.5 years exposure, a total of 12 serious neurologic events in 10 participants were reported for a combined rate of 0.033 events per person-year.

Using the target of 100 person-years of follow-up data collection by the registry networks, the confidence intervals widths and precision of the estimate of 0.033 serious neurologic events per person-year can be calculated based on a Poisson distribution. Table 3 also presents precision for scenarios with higher person-years of follow-up, which may occur depending on actual enrolment into the registry networks, the proportion of patients treated with tofersen treatment, and/or the median follow-up time. In each scenario the precision is reasonably tight.

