### 7.2. Study Rationale and Regulatory Background

This study is part of the planned pharmacovigilance activities for tofersen (tradename: Qalsody™). Qalsody has been approved in multiple regions, including by both the United States Food and Drug Administration (US FDA) (April 2023) and the EMA (May 2024). In Europe, Qalsody was granted marketing authorisation (MA) under exceptional circumstances with the indication of treatment of adults with ALS associated with a mutation in the *SOD1* gene. As part of the conditions of the MA under exceptional circumstances, the marketing authorisation holder (MAH) agreed to conduct and submit the results of this observational registry-based study (Study 233AS401), to further evaluate the long-term safety of tofersen in people living with *SOD1*-ALS. This specific obligation is included as a Category 2 study in the EU risk management plan (RMP).

The safety and efficacy of tofersen was assessed in clinical trials and has a positive benefit/risk profile in the treatment of adults with *SOD1*-ALS. However, information on long-term use is limited. Given this and the rarity of the indication, this non-interventional registry-based study is being conducted as part of the post approval pharmacovigilance activities to further evaluate the long-term safety of tofersen among people with *SOD1*-ALS under routine medical care.

The safety profile is based on 166 participants with ALS (162 with *SOD1*-ALS) that were exposed to any dose of tofersen in the clinical development programs. Of these, a total of

CONFIDENTIAL

The information contained herein may not be used, disclosed, or published without the written consent of Biogen MA Inc.

147 people with *SOD1*-ALS received tofersen 100 mg, for 368.83 participant-years. The median exposure for this group was 148.4 weeks. Most adverse events (AE) reported during treatment with tofersen were consistent with the types and severities of AEs seen in people with *SOD1*-ALS or events observed in the context of the lumbar puncture (LP) procedure.

In the clinical studies, serious neurological events of myelitis, radiculitis, increased intracranial pressure, papilloedema, and aseptic meningitis have been reported in participants receiving tofersen and not in placebo treated participants. Details on these serious reactions are included in the EU product information.

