**Table 3: Study Size Precision Table for Neurological SAEs Based on Observing 0.033 Events Per Person-year**

	Person-years follow-up	Expected Number of Events a	Lower 95	Upper 95	CI width	Precision (CI width/2)
Any Neurologic SAE	100	4	0.0109	0.1024	0.0915	0.0458
	150	5	0.0108	0.0778	0.0670	0.0335
	200	7	0.0141	0.0721	0.0580	0.0290
	250	9	0.0165	0.0683	0.0519	0.0259
	300	10	0.0160	0.0613	0.0453	0.0227

a Rounded up to the nearest integer

The expected study end date may be modified based on study progress, which will be reviewed annually as part of the reassessment procedure.

CONFIDENTIAL

The information contained herein may not be used, disclosed, or published without the written consent of Biogen MA Inc.

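### Table 3 is labelled as precision at 0.033 events per person-year but is computed at rounded-up counts (0.040 in the target row), and the protocol's description of precision as tight does not hold at 100 to 150 person-years

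*Protocol*

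**What the plan says.** Protocol section 9.5 takes its planning rate from the integrated clinical trial population treated at 100 mg: "a total of 12 serious neurologic events in 10 participants were reported for a combined rate of 0.033 events per person-year". Section 7.2 gives the exposure of that group: 147 people "for 368.83 participant-years". Section 9.5 sets the follow-up goal: "the target study size is at least 100 person-years of follow-up from tofersen-treated participants", or alternatively at least 125 cases in total.

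The text then says that interval widths and precision for the 0.033 estimate "can be calculated based on a Poisson distribution". Table 3 carries the title "Study Size Precision Table for Neurological SAEs Based on Observing 0.033 Events Per Person-year" and covers 100 to 300 person-years. It defines precision as half the interval width. A footnote to the expected number of events reads "Rounded up to the nearest integer". The 100 person-year row shows 4 events, limits 0.0109 and 0.1024, and precision 0.0458. The text sums up the table as: "In each scenario the precision is reasonably tight".

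**The concern.** Two things do not fit.

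- The title and the introducing text name one rate for all rows, yet the printed lower limits run 0.0109, 0.0108, 0.0141, 0.0165, 0.0160. At a fixed rate the lower limit should rise steadily with follow-up. Here it falls from 100 to 150 and again from 250 to 300 person-years, which suggests that the rate changes from row to row.
- In the target row the printed half-width, 0.0458, is larger than the rate being estimated. It is hard to call that tight.

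What is at stake is how the study is read. Section 9.5 says that 100 person-years will allow the incidence of serious neurologic events to be evaluated, and the enrolment period and end date are to be reassessed each year. Someone using Table 3 for that purpose should see the interval that belongs to the stated rate, with a description that matches it.

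**Working it through.** **Inputs.** Rate 0.033 per person-year (section 9.5). Follow-up T = 100, 150, 200, 250 and 300 person-years (Table 3). Two-sided 95% limits. Counts rounded up (Table 3 footnote). Trial exposure 368.83 participant-years (section 7.2).

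**The planning rate.** 12 / 368.83 = 0.0325, and 12 / (147 × 2.5) = 0.0327. Both round to 0.033, so the rate is sound.

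**Reproducing Table 3.** With k events in T person-years, the exact Poisson limits are

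lower = χ²(0.025; 2k) / (2T), upper = χ²(0.975; 2k + 2) / (2T).

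For the target row, 0.033 × 100 = 3.30, rounded up to k = 4. The limits are 0.0109 and 0.1024, the width is 0.0915 and the half-width 0.0458, as printed. The other products are 4.95, 6.60, 8.25 and 9.90, rounded up to 5, 7, 9 and 10. With these counts all five rows reproduce to four decimals. Other routes do not reproduce the target row: a normal-approximation half-width at k = 4 is 0.0392, 3.3 events give 0.0423, and 3 events give 0.0407. The table therefore rests on the rounded-up counts.

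**Recomputing at 0.033.** The same formulas at the unrounded expected count k = 0.033 × T give:

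| Person-years | Rate used in Table 3 | Table 3 limits | Table 3 half-width | Limits at 0.033 | Half-width at 0.033 |
|---|---|---|---|---|---|
| 100 | 4/100 = 0.040 | 0.0109–0.1024 | 0.0458 | 0.0075–0.0922 | 0.0423 |
| 150 | 5/150 = 0.033 | 0.0108–0.0778 | 0.0335 | 0.0106–0.0773 | 0.0333 |
| 200 | 7/200 = 0.035 | 0.0141–0.0721 | 0.0290 | 0.0128–0.0694 | 0.0283 |
| 250 | 9/250 = 0.036 | 0.0165–0.0683 | 0.0259 | 0.0145–0.0644 | 0.0250 |
| 300 | 10/300 = 0.033 | 0.0160–0.0613 | 0.0227 | 0.0158–0.0609 | 0.0226 |

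At a constant 0.033 the lower limit rises in every row, so the two falls in Table 3 come from the rounding. In the target row the printed lower limit is 0.0109 / 0.0075 = 1.45 times the value at 0.033, the upper limit is 0.1024 / 0.0922 = 1.11 times, and the half-width 0.0458 / 0.0423 = 1.08 times. At 150 and 300 person-years the rounding hardly matters.

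**Relative precision.** Each half-width is divided by the rate from which it was computed (unrounded values used):

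| Person-years | Table 3, own rate | Recomputed, 0.033 |
|---|---|---|
| 100 | 114% | 128% |
| 150 | 100% | 101% |
| 200 | 83% | 86% |
| 250 | 72% | 76% |
| 300 | 68% | 68% |

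**Comparison with the trial data.** For 12 events in 368.83 participant-years the same formulas give 0.0168 to 0.0568, a half-width of (0.0568 − 0.0168) / 2 = 0.020. That is under half of the target row's half-width on either basis.

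**The case against.** The strongest reply is that nothing here is miscalculated. The footnote discloses the rounding, the count stands next to the person-years in each row, and any reader can divide one by the other. Only whole events can be observed, and no whole number gives exactly 0.033 at 100 person-years; 3 events would be 0.030, with limits 0.0062 to 0.0877. Rounding up also makes the table's own precision measure look worse, not better. All of this stands. The point is a mismatch between label and input, and the footnote does not say that the target row's rate has become 0.040.

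It can also be said that tightness is a matter of judgement, that the protocol sets no criterion for it, and that the study is descriptive in an ultra-rare disease. That has some force at 300 person-years. It does not rescue a statement made for every scenario when the half-width exceeds the rate at the target.

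Three stronger readings are tempting but not supported:

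- *The rounding flatters the design.* Only the lower limit looks better. The upper limit, which matters most for safety, and the half-width both come down on correction.
- *The study size rests on a faulty table.* The target comes from enrolment feasibility: 25 cases a year × 5 years × 40% treated × 2 years = 100 person-years. Section 9.9 says that the target was estimated from recent participant numbers in the registries. Table 3 describes the resulting precision.
- *The Poisson limits are too narrow because 12 events arose in 10 participants.* The protocol does not say how the events were split among those participants, so any inflation factor would be an assumption. It also leaves the calculation of event rates optional, with detail deferred to the SAP.

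**Conclusion.** The point holds and is minor. Table 3 does not show precision at the rate in its title. The target row is an interval for 0.040, and at 0.033 it would be 0.0075 to 0.0922 with half-width 0.0423. The sentence on tightness is unsupported at 100 person-years, where the half-width is 114% or 128% of the rate depending on the basis, and at 150, where it is about equal to the rate. The case against the sentence weakens as follow-up grows, to 68% at 300 person-years.

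This rests on the protocol's own rate and on exact Poisson limits, which reproduce every printed row. Limits at 3.3 events interpolate between whole counts. They lie between the limits for 3 and for 4 events, and the half-width exceeds the rate with either count: 136% of 0.030 for 3 events and 114% of 0.040 for 4.

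The comparison with the trial data gives a sense of scale only. The protocol does not claim to be more precise than the trials, and its stated aim is to evaluate these events under routine care.

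**What to change.** Make three changes in section 9.5:

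1. Recompute Table 3 at 0.033 with chi-square (gamma) limits at the unrounded expected count. Alternatively, keep the rounded counts, add a column with the rate each row uses, and change the title to match.
2. Name the method as exact Poisson limits.
3. Replace the tightness sentence with a factual one. For example: at 100 person-years the 95% interval at 0.033 runs from about 0.008 to 0.092 per person-year, with an upper limit about 2.8 times the planning rate (0.0922 / 0.033 = 2.79), and is wider than the interval of 0.017 to 0.057 from the existing trial data (12 events in 368.83 participant-years).

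The cost is one table and one or two sentences. Data collection, the follow-up target and the planned analyses stay as they are. The abstract repeats neither the table nor the tightness statement, so it needs no change on this point.

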**Table 3: Study Size Precision Table for Neurological SAEs Based on Observing 0.033 Events Per Person-year**

	Person-years follow-up	Expected Number of Events a	Lower 95	Upper 95	CI width	Precision (CI width/2)
Any Neurologic SAE	100	4	0.0109	0.1024	0.0915	0.0458
	150	5	0.0108	0.0778	0.0670	0.0335
	200	7	0.0141	0.0721	0.0580	0.0290
	250	9	0.0165	0.0683	0.0519	0.0259
	300	10	0.0160	0.0613	0.0453	0.0227

a Rounded up to the nearest integer

The expected study end date may be modified based on study progress, which will be reviewed annually as part of the reassessment procedure.

CONFIDENTIAL

The information contained herein may not be used, disclosed, or published without the written consent of Biogen MA Inc.

## 9.6. Data Management

Data on participants are collected during routine encounter-based clinical visits and are entered using electronic case report forms (CRF) by sites participating in the registry networks. Data management is maintained at each registry network according to their internal processes. Provided datasets and tables will be managed according to Biogen processes and in line with all regulations. A summary of the information collected on SAEs, pregnancy, and tofersen treatment is included in Annex 4 (Section 17).

## 9.7. Data Analysis

Planned analyses are summarized below and will be described in more detail in a separate statistical analysis plan (SAP).

Data will be analyzed separately for each registry network. However, the analysis performed will be harmonized as much as possible, where data capture and actual participant and event numbers allow.

Statistical analyses will generally be descriptive in nature and there is no *a priori* hypothesis to be tested. Continuous variables will be described with summary statistics including number of observations, mean, standard deviation, median, first quartile, third quartile, and minimum and maximum values. Categorical data will be described in terms of frequencies and percentages. An additional category of 'missing' will be added to account for missing data. Event rates may also be calculated as deemed appropriate.

All efforts will be made to collect data as completely as possible but incomplete dates could occur and this must be considered when evaluating the event and censoring times. Partial dates with missing information will be imputed as detailed in the SAP.

Analyses will be conducted on all adults with *SODI*-ALS enrolled in Precision-ALS and ALS/MND NHC, including participants treated with tofersen as well as untreated participants. All analyses will be stratified by tofersen treatment status except secondary objective 2 (assessed among tofersen users only). Further details on the exclusion of data from clinical trials and the impact on index dates will be detailed in the SAP.

Comparisons between treated and untreated patients for outcomes related to safety, tolerability, or effectiveness are not planned, owing to the inability to address bias in the analyses, given the small sample size for *SODI*-ALS and uncertainties around patient selection for tofersen treatment.

All participants, including participants who discontinue tofersen, will be followed until death or loss to follow-up. Sensitivity analyses will be performed censoring data 150 days (5 half-lives) after tofersen discontinuation (after which data will then be excluded from the analysis) [Benet and Zech 1981; FDA 2003; Rowland and Tozer 2010].

Data collected while a person with *SODI*-ALS is participating in an interventional clinical trial (with tofersen or any other investigational medicinal product) will be excluded since this study will focus on real-world data and the results from interventional clinical trials will be available elsewhere.

CONFIDENTIAL

The information contained herein may not be used, disclosed, or published without the written consent of Biogen MA Inc.

The analysis population and definition of index date for statistical analysis will differ by treatment status and by study objective. In general terms, index date will be the date of tofersen treatment for data from participants in the treated group or date of enrolment into the registry for data from participants in the untreated group [REDACTED]

[REDACTED] Sensitivity analyses will be performed excluding retrospectively treated participants (i.e., those who initiated tofersen treatment prior to enrolment in the registry networks).

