#### **9.7.1.2. SAEs**

Frequency of all reported SAEs will be summarized and presented by Medical Dictionary for Regulatory Activities (MedDRA) system organ class (SOC)/preferred term (PT) or International Classification of Diseases (ICD), as appropriate. Event rates may also be calculated if deemed appropriate.

The analysis of SAEs will be based on data collected only after implementation of SAE reporting forms and thereby the index date will be defined as the latter of tofersen initiation, registry enrolment, or implementation of SAE forms as appropriate, and the analysis population will consist of participants who are still alive at SAE form implementation.

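### Table 3 states precision for a rate combined over both registry networks, but Section 9.7 analyses each network separately and leaves event rates optional

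*Protocol*

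**What the plan says.** Section 9.5 (Study Size) counts enrolment over the two networks together: "approximately 125 cases could be expected across both registry networks". With "Assuming a median follow-up time of approximately 2 years" and "an estimate of 40% tofersen treatment proportion, 100 person-years of follow-up data could be expected among tofersen-treated participants", it sets a target of at least 100 treated person-years or 125 cases in total. The precision calculation uses that total: "Using the target of 100 person-years of follow-up data collection by the registry networks". Table 3 gives Poisson 95% limits for a single composite, any neurologic SAE, at 100 to 300 person-years, and the text before it calls the precision adequate in every scenario. The assumed rate comes from the integrated clinical studies: "a total of 12 serious neurologic events in 10 participants were reported for a combined rate of 0.033 events per person-year".

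Section 9.7 (Data Analysis) sets the unit of analysis: "Data will be analyzed separately for each registry network". The only qualification is that the two analyses will be harmonised as far as the data allow. No combined estimate appears in the visible text. On SAEs, Section 9.7.1.2 plans frequencies by MedDRA or ICD category and adds: "Event rates may also be calculated if deemed appropriate". Section 9.7 has a similar optional sentence about rates in general.

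**The concern.** The study-size section and the analysis section do not match on two points.

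- **Unit.** The sizing adds the two networks; the analysis keeps them apart.
- **Commitment.** The sizing rests on an incidence rate per person-year with an interval; the analysis section only permits a rate.

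Primary objective 2 covers the serious neurologic events, and Section 7.2 names their evaluation as one of the main aims. The study is a specific obligation of the marketing authorisation. A reader of Section 9.5 would expect the final report to contain a rate with roughly the Table 3 interval. Under Section 9.7 as written, the report could contain two sets of frequencies, or two rates that are each clearly less precise than stated. Leaving the rate optional also means that the decision to report it can be taken after the events have been seen.

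**Working it through.** **Inputs**

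- Clinical-study rate (Section 9.5): 0.033 per person-year. Check against Section 7.2, where 147 participants "received tofersen 100 mg, for 368.83 participant-years": 12 / 368.83 = 0.0325, close to the stated value.
- Treated person-years (Section 9.5): 25 cases per year × 5 years × 0.40 × 2 years = 100, over both networks.
- Table 3 event count: 0.033 × person-years, rounded up.
- Split of person-years between networks: not given. The splits below are assumptions.

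**Formulas**, for x events in T person-years:

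- lower limit = χ²(0.025; 2x) / (2T)
- upper limit = χ²(0.975; 2x + 2) / (2T)
- half-width = (upper − lower) / 2
- chance of no event = exp(−0.033 × T)

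**Step 1: reproduce Table 3.** At T = 100, 0.033 × 100 = 3.3, rounded up to 4. The limits are 0.0109 and 0.1024, the width 0.0915 and the half-width 0.0458, as printed. The other four rows (150, 200, 250 and 300 person-years) also reproduce to four decimals. The table is arithmetically correct for combined data.

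**Step 2: same method, same 100 person-years, one network at a time.**

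| Assumed split | Person-years | Expected events | Events used (rounded up) | 95% interval | Half-width | Chance of none |
|---|---|---|---|---|---|---|
| Combined | 100 | 3.3 | 4 | 0.0109–0.1024 | 0.0458 | exp(−3.3) = 0.04 |
| 50:50, each | 50 | 1.65 | 2 | 0.0048–0.1445 | 0.0698 | exp(−1.65) = 0.19 |
| 75:25, smaller | 25 | 0.825 | 1 | 0.0010–0.2229 | 0.111 | exp(−0.825) = 0.44 |
| 90:10, larger | 90 | 2.97 | 3 | 0.0069–0.0974 | 0.0453 | exp(−2.97) = 0.05 |
| 90:10, smaller | 10 | 0.33 | 1 | 0.0025–0.5572 | 0.277 | exp(−0.33) = 0.72 |

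At 50:50 the ratio to the stated figure is 0.0698 / 0.0458 = 1.52. Of the splits examined (50:50, 60:40, 70:30, 80:20 and 90:10, plus the smaller network at 75:25), only 90:10 brings the larger network to the Table 3 figure.

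**Step 3: is this an effect of rounding up?** Putting the unrounded expected counts into the same formulas gives half-widths of 0.0423 (3.3 events in 100 person-years) and 0.0652 (1.65 in 50). The ratio is 0.0652 / 0.0423 = 1.54, so rounding does not explain the loss.

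**Step 4: read the loss from Table 3 itself.** With 200 person-years split evenly, each network has the 100-person-year row: 0.0458 instead of 0.0290. With 300, each has the 150-person-year row: 0.0335 instead of 0.0227.

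**The case against.** The strongest reply is that Section 9.7 is a summary and defers detail to a separate SAP, which is not shown and may well contain a rate table. This has force for the composite definition, the interval method and the coding dictionary, which can properly wait for the SAP. It has less force for the unit of analysis. The protocol does not leave that open; it states separate analysis, so a combined rate in the SAP would depart from it. Parts of Section 9.7 are redacted, but the sentences on separate analysis and optional rates are complete.

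Separate analysis is also defensible. Section 9.9 describes heterogeneity across sites, and each network keeps its own processes. This stands as a reason to show network-specific results. It does not make a combined precision table describe them.

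The target is also a minimum. If treated follow-up reached 200 person-years with an even split, each network would have the 100-person-year precision. The stated target is nevertheless 100 in total.

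Three stronger readings are tempting, and the protocol does not support them:

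- **That primary objective 2 cannot be answered.** The objective is descriptive, and Section 9.9 plans a review of individual SAEs for relatedness, timing to dosing and consistency with trial data. Separate tables do not prevent this.
- **That nothing could be set against the clinical-study rate.** No formal comparison is planned. If network rates are calculated they can be placed beside 0.033, only imprecisely.
- **That the networks will code events in different dictionaries.** Section 9.7.1.2 allows MedDRA or ICD but does not say that the networks will differ.

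**Conclusion.** The mismatch is real and narrow. The Table 3 half-width of 0.0458 belongs to a rate combined over both networks. The protocol plans separate analyses, names no combined estimate and does not commit to a rate. For the stated target of 100 treated person-years, per-network precision would be about 1.5 times worse at an even split, and worse still for the smaller network at an uneven one. These sizes rest on assumed splits and on the clinical-study rate of 0.033 applying in routine care.

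No estimate is biased and no test depends on the point. A reader might infer that no planned analysis could ever deliver the stated precision. That goes too far while the SAP is unseen and rates remain permitted. The supported conclusion is that the protocol's precision statement does not match its own analysis section. This should be fixed, preferably before data extraction starts.

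**What to change.** In Sections 9.7 and 9.7.1.2, state that for tofersen-treated participants the incidence rate of any serious neurologic event will be calculated by summing events and at-risk person-years over both networks. Give it with an exact Poisson 95% interval and show the network-specific rates beside it. For this endpoint, replace the permissive wording on rates with a commitment. Aggregate counts and person-years from each network suffice, so individual records need not be merged and the other analyses can stay separate.

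If the networks are not to be combined, restate Table 3 per network under stated splits of person-years, and revise the sentence in Section 9.5 that describes the precision as adequate in every scenario.

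The cost is a few sentences and one extra table. The combined rate averages over differences in ascertainment between the networks; the network-specific rows will show them.
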